**IRB Number:** **852479**

## Background and Study Rationale

### 1 Introduction

This document is a research protocol. This study will be conducted in full accordance with all applicable University of Pennsylvania Research Policies and Procedures and all applicable Federal and state laws and regulations including the following regulations as they apply 45 CFR 46, 21 CFR Parts 50, 54, 56. All episodes of noncompliance will be documented.

The Federal Aviation Administration (FAA) is interested in how aircraft noise at night affects the sleep and health of residents living in the vicinity of airports, and how any negative effects can be mitigated. The goal of this project is to investigate the effects of different kinds of aviation noise (AN) on sleep under controlled laboratory conditions, and to investigate whether some of the sleep disturbing effects can be mitigated by introducing a type of broadband noise (BN) known as pink noise into the bedroom or by wearing earplugs (EP). The sleep of 24 subjects will be monitored with polysomnography, actigraphy and ECG over 7 nights. Subjects will fill out surveys, and perform cognitive, driving simulation and hearing tests in the evening before bed and in the morning after waking up. Blood will be drawn each morning to identify changes in gene expression induced by the experimental conditions. Subjects will be investigated in groups of 4 in the Chronobiology Isolation Laboratory (CIL) in the Hospital of the University of Pennsylvania. This newly constructed facility includes 4 acoustically isolated bedrooms and a high-fidelity sound system.

#### 1.1 Background and Relevant Literature

Undisturbed sleep of sufficient duration and quality is of paramount importance for recuperation and health. Aircraft noise has been shown to disturb sleep and be associated with long-term health consequences like cardiovascular disease. While sound insulation can lower noise levels in the bedroom, it is expensive and only residents living close to the airport are eligible for compensation for sound insulation. Furthermore, residents often fail to close windows during the night to increase ventilation and decrease bedroom temperatures, which renders the sound insulation measures ineffective. Therefore, the identification of inexpensive and effective interventions to reduce the adverse effects of aviation noise on sleep is warranted.

Broadband noise (BN) is a promising and inexpensive intervention that could help mitigate the negative effects of aviation noise on sleep for large parts of the population that are either ineligible for sound insulation or still suffering from aviation noise-induced sleep disturbance despite sound insulation. This study will be the first to investigate – using the gold standard measure of sleep, polysomnography – the effectiveness of BN in mitigating the sleep-disturbing effects of aviation noise. Machines and apps that produce BN (e.g., white noise) are very popular (>200 different sound masking apps exist that have been downloaded >10 million times), but according to our own systematic review of the literature rigorous studies corroborating the sleep promoting effects of BN are missing. Also, as continuous BN exposure during the night could affect hearing, it will be important to assess temporary hearing threshold shifts after BN exposure nights.

This study will investigate whether BN promotes or disturbs sleep in an otherwise noise-free environment and whether BN played back at two different sound levels mitigates the negative effects of aviation noise on sleep. Furthermore, this study will evaluate the effectiveness of earplugs, an inexpensive method to reduce perceived noise levels, as a countermeasure to aviation noise. To date, earplugs have been mostly studied as noise countermeasures in intensive care units; one study in 40 participants investigated the effects of earplugs and eye masks in a simulated ICU environments (noise and light) and found sleep protective effects of this combined intervention. To our knowledge, no study has investigated the effectiveness of earplugs on mitigating aviation noise effects on sleep.

In addition to jet engine noise, we plan to investigate noise from new aviation noise sources that are either under-studied (i.e., helicopter noise) or emerging as important new noise sources (i.e., noise from drones and low sonic booms). This project will thus help assessing the relative impact of these under-studied and new aviation noise sources relative to jet engine noise. We will also play back an alarm sound and the sound of a baby crying, as one of the negative consequences of broadband noise and earplugs may be that these important events are missed.

## **2 Study Objectives**

The overall objective of this study is to investigate how different kinds of aviation noise affect polysomnographically assessed sleep, whether these effects can be mitigated by BN exposure at two different intensities or by earplugs, whether these countermeasures affect the perception of relevant sounds (i.e., alarm, baby crying), and whether the different kinds of aviation noise differ in their sleep disturbing properties. The study will also investigate how any aviation noise-induced sleep disturbance affects next day performance, hearing thresholds, gene expression and self-reported well-being (see 3.4).

### **2.1 Primary Objective**

The primary objective of this study is to investigate whether BN exposure at two intensities or wearing earplugs mitigates the negative consequences of aviation noise on sleep.

### **2.2 Secondary Objectives (if applicable)**

- To investigate the effects of the different noise conditions (see 3.1) on next day cognitive and driving simulator performance, gene expression in the blood, hearing thresholds, and subjective well-being.
- To investigate in an event-related analysis whether the different sources of aviation noise (e.g., jet engine, helicopter, drone, low sonic boom), at the same maximum sound pressure levels, differ in their potential to arouse subjects from sleep, and whether BN and EP differ in their potential to mitigate the arousing effects of the different kinds of aviation noise on sleep.
- To investigate to what degree BN and EP prevent arousal to meaningful sounds like alarms or a crying baby.

## **3 Investigational Plan**

### **3.1 General Design**

Subjects will be screened in two screening sessions to determine study eligibility prior to participating in the in lab protocol. The sleep of 24 subjects will be monitored with polysomnography over 7 consecutive nights in groups of 4 where the entire group has been randomly assigned to 1 of 6 noise exposure condition patterns.

After an adaptation night, subjects will be exposed to:

1. Control night without any noise exposure and without earplugs (CTRL);
2. Aviation noise only (AN);
3. Broadband (pink) noise 50 dBA only (BN50);
4. Aviation noise plus earplugs (AN+EP);
5. Aviation noise plus broadband (pink) noise 40 dBA (AN+BN40);
6. Aviation noise plus broadband (pink) noise 50 dBA (AN+BN50).

We will investigate participants in 6 groups of 4 subjects each (we also plan for a reserve 7th study run to account for study drop-outs). Each group will be exposed to the same condition in each study night. Each subject will receive each exposure – in a randomized and balanced fashion – according to the randomization table in 3.2.

### Noise Exposure

The AN nights will consist of up to 120 noise events with maximum sound pressure levels  $L_{AS,max}$  of 45, 50, 55, 60 and 65 dB, including noise from jet engine aircraft, helicopters, drones, and low sonic booms. The jet engine noise events will be identical to events used in a prior study at the German Aerospace Center (DLR) and another study on broadband sounds on sleep performed by collaborator [name] in Sweden, which allows for a direct comparison to these studies. We will choose a few events within each dB category and repeatedly play those back. Due to the limited sample size, playing every event back only once would not provide us with enough data for averaging. We will also include an alarm sound and/or sound of a baby crying, as a potential caveat of using EP/BN is that meaningful sounds may be missed. The sequence and spacing of noise events will be identical within a study group but different across study groups. Noise scenarios will be pre-programmed. They will be started at the next full minute after lights out. Planned lights out is 11 pm and planned lights on is 7 am (i.e., 8 hour sleep opportunity).

### Evening and Morning Procedures

Subjects will arrive in the lab around 8 pm in the evening and they will be able to leave the lab around 9 am in the morning (by 10 am at the latest). As our noise exposures can affect sleep and impair recuperation to some degree, participants will be informed in the consent form that they should not operate heavy machinery during the study. We will also offer a cab for those who would otherwise use a car to come to the lab. We will provide snacks in the evening and a light breakfast in the morning. Subjects can shower in the morning (after all tests) if they wish.

In the evening (before bed) and in the morning (after waking up), subjects will do the following:

- (1) Blood draw (for gene expression analyses to be performed by the FAA Civil Aerospace Medical Institute (CAMI); morning only).
- (2) Fill out surveys that ask about sleepiness, mood states, the previous day or the previous night;
- (3) Cognition test battery (10 cognitive tests);
- (4) Driving simulator task;
- (5) Hearing test;
- (6) Blood pressure measurement; and
- (7) Resting ECG measurement.

### 3.2 Allocation to Interventional Group

We will investigate participants in 6 groups of 4 subjects each. Each subject of a group will be exposed to the same condition in each study night, and each subject will receive each exposure— in a randomized and balanced fashion – according to the randomization table below.

Group	Night 1	Night 2	Night 3	Night 4	Night 5	Night 6	Night 7
1	Adaptation	A	B	C	D	E	F
2	Adaptation	B	D	A	F	C	E
3	Adaptation	C	A	E	B	F	D
4	Adaptation	D	F	B	E	A	C
5	Adaptation	E	C	F	A	D	B
6	Adaptation	F	E	D	C	B	A

Please note that in this randomization paradigm, each exposure appears in each position exactly once, and is preceded by each other exposure exactly once. The letters A-F will be randomly assigned to the exposure conditions 1-6 listed in 3.1 above by the principal investigator using a random number generator. Study participants and staff will be blinded to the condition of each night. Staff will only be unblinded after the start of the measurements each night (i.e., after subjects went to bed) so that the correct playback of the conditions can be monitored.

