### **Sleep Measurements**

Subjects' sleep will be measured polysomnographically (PSG) with the Prodigy system, which includes frontal electroencephalogram (EEG) electrodes, an electrooculogram (EOG) and a submental electromyogram (EMG). Data will be transmitted wirelessly to a bedside tablet. The tablet will also record sound pressure levels that will help synchronize PSG and acoustic data. Subjects will also wear a Bittium Faros device that measures the ECG (1 kHz) and body movements (25 Hz).

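### Does the broad blinding statement in section 3.2, with no stated masking of sleep scoring, call for a change to the plan?

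*Combined protocol and SAP*

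**What the plan says.** Section 3.2 (Allocation to Interventional Group) makes a general claim: "Study participants and staff will be blinded to the condition of each night". The sentence after it limits the claim for staff: "Staff will only be unblinded after the start of the measurements each night (i.e., after subjects went to bed"), the reason given being that playback has to be monitored.

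Section 3.1 lists six conditions. The control is described as "Control night without any noise exposure and without earplugs (CTRL") and the earplug arm as "Aviation noise plus earplugs (AN+EP"). No other condition uses earplugs, and no sham is mentioned. On the timing of the noise scenarios, the Noise Exposure text of 3.1 says: "They will be started at the next full minute after lights out".

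The primary objective in 2.1 asks "whether BN exposure at two intensities or wearing earplugs mitigates the negative consequences of aviation noise on sleep". A secondary objective in 2.2 covers, among other things, "gene expression in the blood, hearing thresholds, and subjective well-being".

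The primary endpoint (3.4.1) is time in slow wave plus REM sleep. The Sleep Measurements text of 3.3 names the recording system and its signals and adds: "The tablet will also record sound pressure levels that will help synchronize PSG and acoustic data". Section 8.2 describes transfer of de-identified recordings through the polysomnography system's server. Neither states a staging method or any masking of a scorer. Section 14 lists Study Procedures as a separate attachment.

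**The concern.** A person wearing earplugs knows it, and a person who hears aircraft or pink noise before falling asleep knows that too. Staff are told the condition every night, before any of the morning measures. What is left is non-disclosure up to bedtime, which is less than the sentence in 3.2 says. A reader who took that sentence at face value would think the comparison of earplugs with aviation noise alone, one of the three mitigation comparisons, was made with participants unaware of condition. Awareness would matter most for self-reported well-being.

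The second part touches the primary endpoint. Sleep staging and arousal scoring can involve judgement. De-identification hides the person, not the condition. If a scorer knew the condition, or could see the sound-level record stored with the recording, expectation could shift the result, and this is a step where masking is achievable.

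**Working it through.** **1. The plan's own figure.** The blinding claim carries no number. The nearest is the power statement in 6.1: 24 subjects, effect size 0.60, two-sided 5%, at least 80% power. Section 6.3.2 equates the primary contrast with a paired t-test. Reading 0.60 as the mean paired difference divided by the SD of the paired differences (an assumption), df = 24 − 1 = 23, the noncentrality is 0.60 × √24 = 2.94, and the noncentral t distribution gives 80.4%. The figure reproduces. Section 6.2 identifies the powered contrast as aviation noise with and without broadband noise at 50 dB, and neither of those nights uses earplugs.

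**2. Participants.**
- Exposure nights: 24 subjects × 6 conditions = 144.
- Earplug nights: 24 × 1 = 24, and 24/144 = 1/6.
- Mitigation comparisons against aviation noise alone: broadband noise at 40 dBA, broadband noise at 50 dBA, and earplugs. Earplugs enter one of the three.

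For these nights the sentence in 3.2 cannot be literally true. For the audible conditions, playback begins within about a minute of lights out, so masking cannot be assumed. In both cases what the participant perceives is the exposure under study. Removing the perception would remove the intervention.

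**3. Staff.** There are 6 groups × 6 exposure nights = 36 group-nights, and staff are unblinded on all 36, as 3.2 says. What could that knowledge alter?
- *Exposure:* nothing. Scenarios are pre-programmed, everyone in a group gets the same condition, and the printed table fixes the order. Checked against the table, each letter falls once in each of the six positions. The 6 × 5 = 30 adjacent pairs are all different, which covers all 6 × 5 = 30 possible ordered pairs, so the balance claimed in 3.2 is correct. Every participant receives every condition, so membership of a group determines only the order.
- *Morning measures:* little. Cognition runs on a laptop, driving on a simulator and audiometry through a headphone system, and RNA is analysed elsewhere. Staff take blood pressure, but it is not among the endpoints listed in 3.4.2.

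**4. Scoring.** Taking the relevant places together:
- 3.3 and 5.2.1 say that sleep is recorded, and 3.3 names the device.
- 8.2 says how the files move and that they are de-identified.
- 3.4.1 and 3.4.2 say what is derived from them.
- None of them says whether staging is manual or automated, who does it, or what that person can see.

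The 24 × 7 = 168 recordings (144 of them on exposure nights) therefore have no stated scoring rule in this document. Nor does any sentence say that night staff stage the sleep, that staging is unmasked, or that a scorer sees the sound record. The stated purpose of that record is synchronization. The endpoints also differ in their dependence on staging: spectral power is computed from the signal, whereas slow wave plus REM time depends directly on staging.

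**5. Size of any bias.** The documents give no scoring error, no agreement between scorers and no time at which earplugs are handed out. Any bias or false-positive rate would only restate whatever shift was assumed, so none is given.

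**The case for a change.** The strongest case for a change is that participant awareness cannot be prevented but scorer awareness can. The endpoint at risk is the primary one, and the remedy is a single sentence: automated staging without condition input, or a masked scorer working from coded files with the sound record withheld. A publication that repeated 3.2 unqualified would also misdescribe the comparison of earplugs with aviation noise alone.

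Two parts of this stand. The sentence in 3.2 is too broad for participants wearing earplugs, and the text names no staging method.

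The rest does not carry through to a change. On staff, the two sentences in 3.2 are consecutive, and the second gives both the time of unblinding and its reason. That is a disclosed trade-off, since someone has to confirm that the right condition is playing. On participants, rewording would alter no procedure, analysis or result, and 3.1 already shows any reader what each condition involves. On scoring, the case rests on silence. If staging is automated without condition input, there is no scorer to mask. If it is manual, the rule may stand in the Study Procedures attachment, which is not part of this document. Leaving such a step to operating procedures is a gap in reporting and does not show that the step is done badly.

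**Conclusion.** The observation is accurate but leads to no change in the plan. The blinding statement overreaches for earplug wearers on 24 of 144 participant exposure nights and cannot be assumed to hold for audible conditions once playback starts. Staff unblinding on all 36 group-nights is disclosed and cannot affect exposure. The stated power (80.4% on recalculation), the sequences and the analysis are unaffected.

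The scoring question is missing detail that the study team can fill sensibly when it describes its methods: how sleep was staged, and whether condition was hidden from any scorer. The same description can present the design as non-disclosure until bedtime, with the earplug condition open to its wearer.

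This conclusion rests on two assumptions: that staging is automated without condition input or follows a masked procedure held outside this document, and that nobody relies on 3.2 to claim participant blinding for self-reported outcomes. Evidence that a scorer knew the condition would reopen the point for the primary endpoint. The documents contain none.

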### 3.3 Study Measures

During the **telephone screening** session, the following surveys will be completed on sleep disorders for eligibility assessment:

1. Cambridge-Hopkins Restless Leg Syndrome Questionnaire;
2. Insomnia\_Severity Index;
3. STOP BANG Questionnaire as a measure of sleep apnea.

During the two **in-office screening** sessions, the following measures will be completed:

### **Surveys**

1. Epworth Sleepiness Scale as a measure of fatigue;
2. SF36-Health Survey as a measure of general health;
3. Positive and Negative Affect Schedule (PANAS) as a measure of affect.
4. Profile of Mood States Short Form (POMS-SF) as a measure of mood states.
5. Beck Depression Inventory (BDI-II) as a measure of depression.
6. Beck Anxiety Inventory (BAI) as a measure of anxiety.
7. Horne-Ostberg Morningness-Eveningness Questionnaire;
8. Karolinska Sleepiness Scale; and
9. Pittsburgh Sleep Quality Index as a measure of quality and patterns of sleep.

#### *Survey Information*

The Cambridge-Hopkins Questionnaire (CH-RLSq) (Allen & Burchell, 2008) is a diagnostic self-report tool of 13 questions used to ascertain restless leg syndrome (RLS) and to exclude similar conditions that mimic RLS such as leg cramps. Subjects will complete this once, during the telephone screening, in order to determine initial eligibility by ruling out exclusionary criteria of sleep disorders.

The Insomnia Severity Index (ISI) (Morin, 1993) is a set of 7 questions using a range of 0-4. Scores between 15-21 suggest moderate clinical insomnia, while scores >21 suggest severe cases. Subjects will complete this once, during the telephone screening, in order to determine initial eligibility by ruling out exclusionary criteria of sleep disorders.

The STOP BANG Questionnaire (Chung, 2008) is used to measure risk of sleep apnea. The 8 Yes/No questions ask about snoring, daytime sleepiness, obstructive breathing, blood pressure, BMI, age, neck circumference and gender. Scores of 3-4 suggest intermediate risk of Obstructive Sleep Apnea, while scores in the 5-8 range suggest high risk of OSA. Subjects will complete this once, during the telephone screening, in order to determine initial eligibility by ruling out exclusionary criteria of sleep disorders.

The Epworth Sleepiness Scale (ESS) (Johns, 1991) is a measure of fatigue by asking likelihood of dozing in 8 different situations. Responses range from 0 [no chance of dozing] to 3 [high chance of dozing] for each prompt. Scores between 10-15 suggest excessive sleepiness, and over >15 that may require medical attention. Subjects will complete this once, at the first in-person screening, to rule out excessive tiredness that may interfere with their ability to maintain the requirement of limited daytime naps during the study.

The Short Form Health Survey (SF-36) (Ware et al., 1993) is a 36-item self-report measure used as an indicator of general wellness. An algorithm is used to assign values to each response, generating a mental health score and a physical health score. Subjects will complete this once, at the first in-person screening, to determine their fitness to proceed with the study.

The Positive and Negative Affect Schedule (PANAS) (Watson et al., 1988) lists a set of 20 emotions and moods, and asks how often the subject experienced each in the past week. An algorithm is used to generate Positive and Negative Affect Scores, where higher scores represent higher levels of the respective affects. Subjects will complete this during their in-person screening to establish baseline scores and again twice daily as part of their morning and evening surveys during the in-lab study to see the effects of the interventions.

The Profile of Mood States (POMS-SF) (Shacham, 1983) asks to what extent subjects are experiencing each of 37 emotions, moods or affects at that moment. Responses are scored using an algorithm, resulting in 6 sub-scores, with 4 representing negative affect: Tension, Anger, Fatigue, Depression and Confusion, and 2 representing positive affect: Esteem-Related Affect and Vigor. A Total Mood Disturbance score is then generated by summing the negative sub-scores and subtracting the positive sub-scores. Subjects will complete this during their in-person screening to establish baseline scores and again twice daily as part of their morning and evening surveys during the in-lab study to see the effects of the interventions.

The Beck Depression Inventory (BDI-II) (Beck, 1996) is a common self-report tool used to evaluate the severity of depression. Subjects respond to 21 questions related to clinical symptoms of depression using a scale of 0-3, where higher scores represent higher depression. Scores between 14-19 suggest mild depression, 20-28 moderate, and 29-63 severe. Subjects will complete this during their in-person screening.

The Beck Anxiety Inventory (BAI) (Steer & Beck, 1996) asks how often a subject has experienced 21 symptoms associated with anxiety in the past month on a scale of 0 to 3, with higher scores representing more often occurrences. Responses are summed, with scores of 22-35 suggesting moderate anxiety and scores 36-63 suggesting severe anxiety. Subjects will complete this during their in-person screening.

The Morningness-Eveningness Questionnaire (MEQ) (Horne & Östberg, 1976) asks 19 questions about daily sleep-wake activities and time preferences in order to assess a subject's circadian rhythm. Responses are assigned values, which are summed and used to indicate on a sliding scale whether a subject falls towards being an 'evening' type (scores of 16-30) or a 'morning' type (70-86). Subject will complete this once, at their first in-person screening, in order to establish their chronotype.

The Karolinska Sleepiness Scale (Åkerstedt & Gillberg, 1990) is one-question scale asking a subject to rate their current sleepiness. The scale is 1 to 9, with 1 labeled 'extremely alert', 5 as 'neither alert nor sleepy', and 9 as 'very sleepy, great effort keeping awake, fighting sleep'. Subjects will complete this at their first in-person screening and twice daily as part of their morning and evening surveys during the 7-night in-lab study for an acute tracking of subjective sleepiness.

The Pittsburgh Sleep Quality Index (PSQI) (Buysse, 1989) is a set of 19 questions to assess sleep quality and patterns over a given time period. It asks questions about bed time, wake time, sleep latency, use of sleep medication and how often certain occurrences have caused sleep disturbances and affected daytime activities in the past month. Subjects will complete this at their first in-person screening and once daily as part of their morning survey during the 7-night in-lab study to log their sleep quality during the noise interventions.

Subjects will receive a pulse oximeter during the first screening session. They will wear this device for one night. Subjects with multiple relevant dips in blood oxygen saturation will be ineligible to participate in the study due to suspected sleep apnea.

Subjects will also receive a wrist actiwatch that measures movement activity and provides information on sleep-wake activity. They will be instructed to wear it 24/7 and only take it off during showers/swimming or while doing contact sports. Additionally, subjects will fill out a sleep log every morning (online if possible). Subjects will start wearing the actiwatch and filling out the sleep log after first screening and continue until the end of the in-lab study or until ineligibility is determined.

We will also perform a hearing test (see below) during first screening. Subjects will be familiarized with the driving simulator in the first screening and the cognitive tests during the second screening session.

During the **7-night in-lab portion** of the study, the following measures will be performed:

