### **AM and PM Surveys**

Subjects will complete a survey once in the evening before bed and another in the morning before departure. These surveys include questions about sleep duration and quality, daytime activities outside of the lab (e.g. napping, exercise and caffeine intake), mood states, positive and negative affect, and other general questions about fatigue. It takes approximately 10 minutes to complete each survey, for a total of 20 minutes daily. The morning questionnaire involves the POMS, PANAS, Karolinska Sleepiness Scale (KSS), and parts of the Pittsburgh Sleep Quality Index (PSQI) that specifically address the quality of sleep during the preceding night. The evening questionnaire includes the POMS, PANAS and KSS.

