## **5.2 Study Intervention Phase**

### **5.2.1 In-Laboratory Phase**

The **in-laboratory phase** consists of 7 consecutive overnights. Subjects will wear a wrist actiwatch that measures movement activity 24/7 during the in-laboratory phase. The sleep of approximately 24 subjects will be monitored with polysomnography over 7 consecutive nights in groups of 4 in the Chronobiology Isolation Laboratory (CIL) in the Hospital of the University of Pennsylvania where the entire group has been randomly assigned to 1 of 6 noise exposure condition patterns (see 3.2 above).

After an adaptation night, subjects will be exposed to one of the following in each night:

1. Control night without noise and without earplugs (CTRL);
2. Aviation noise only (AN);
3. Broadband (pink) noise 50 dBA only (BN50);
4. Aviation noise plus earplugs (AN+EP);
5. Aviation noise plus broadband (pink) noise 40 dBA (AN+BN40);
6. Aviation noise plus broadband (pink) noise 50 dBA (AN+BN50).

The aviation noise night is described in greater detail in 3.1. We will investigate participants in 6 groups of 4 subjects each. Each group will be exposed to the same condition in each study night. Each subject will receive each exposure in a randomized and balanced fashion.

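### As described, the in-lab PANAS has a past-week recall window while the condition changes every night, so its condition contrasts would be attenuated; the in-lab window should be stated

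*Combined protocol and SAP*

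**What the plan says.** Section 3.3, Survey Information, says that the PANAS "lists a set of 20 emotions and moods, and asks how often the subject experienced each in the past week". Subjects complete it at screening for baseline scores and "again twice daily as part of their morning and evening surveys during the in-lab study to see the effects of the interventions". Both the AM and PM Surveys text in 3.3 and section 5.2.1 list the PANAS in the morning and evening questionnaires. Neither gives it a different time frame.

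Sleep is "monitored with polysomnography over 7 consecutive nights in groups of 4" (3.1). Section 5.2.1 adds: "After an adaptation night, subjects will be exposed to one of the following in each night". Section 3.2 describes a square in which "each exposure appears in each position exactly once, and is preceded by each other exposure exactly once". No washout night is planned.

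The secondary objectives in 2.2 include condition effects on next-day cognitive and driving performance, "gene expression in the blood, hearing thresholds, and subjective well-being". Section 3.4.2 lists no survey score as an endpoint.

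The other repeated instruments have short windows:
- The PSQI is described with a past-month window, but its in-lab use is limited to "parts of the Pittsburgh Sleep Quality Index (PSQI) that specifically address the quality of sleep during the preceding night".
- The POMS-SF is described as momentary.
- The KSS asks about current sleepiness.

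Section 3.1, Evening and Morning Procedures, says in general terms that the surveys cover sleepiness, mood, and the day or night before. It does not name the PANAS.

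**The concern.** A question about the whole past week cannot isolate one night's exposure when the exposure changes nightly. Answers given after later nights blend the latest condition with those before it, so carry-over is built into the question. The protocol shortens the window for the PSQI but says nothing equivalent for the PANAS.

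At stake is the PANAS contribution to the subjective well-being objective. If the form follows the description, differences between conditions shrink, and a small or null PANAS contrast would be hard to interpret. A recall window cannot be repaired after the data are collected.

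**Working it through.** **Plan's own figure.** Section 6.1 states at least 80% power for N = 24, effect size 0.60, two-sided 5%. Section 6.3.2 equates the primary contrast with a paired t-test. The noncentral t distribution gives 80.4%, so the figure reproduces. It belongs to SWS+REM duration; the plan gives no PANAS figure.

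**Which scores mix conditions.** A seven-night window ending the morning after study nights 2, 3, 4, 5, 6 and 7 holds 1, 2, 3, 4, 5 and 6 experimental conditions. The rest is the adaptation night and 5 down to 0 home nights. Counting all 14 in-lab scores (7 evenings, 7 mornings):
- No condition: evening 1, the morning after night 1, evening 2 (3 scores).
- One condition: the morning after night 2, evening 3 (2 scores).
- Two or more conditions: the remaining 14 - 5 = 9 scores.

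**Structure of the square (3.2).** The rows are ABCDEF, BDAFCE, CAEBFD, DFBEAC, ECFADB, FEDCBA. Rows 4, 5 and 6 are rows 3, 2 and 1 reversed. Any ordered pair of conditions therefore occurs, earlier before later, in exactly 3 of 6 rows.

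**Retained contrast.** Assume that a morning score is a weighted mean of seven nights, with weight w on the latest and (1-w)/6 on each of the six earlier nights. Let t(X) be the one-night effect of condition X. Averaged over the six rows, the score for X is

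w·t(X) + (3/6)·[(1-w)/6]·(sum of t over the other five conditions) + a constant.

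The constant holds the adaptation and home nights. It is the same for every condition because each condition occupies each position once. Subtracting the same expression for condition Z gives

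[w - (1-w)/12]·[t(X) - t(Z)].

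The balance of the square does not remove the attenuation: a condition never precedes itself, so its effect enters its competitors' scores half the time. The analysis in 6.2, carried over to secondary outcomes in section 6, has a random subject intercept and names no carry-over term.

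| Weight on latest night, w | w - (1-w)/12 | Share kept |
|---|---|---|
| 1/7 (equal weights) | 1/7 - 1/14 = 1/14 = 0.071 | 7% |
| 0.3 | 0.3 - 0.058 = 0.242 | 24% |
| 0.5 | 0.5 - 0.042 = 0.458 | 46% |
| 0.7 | 0.7 - 0.025 = 0.675 | 68% |
| 1 (latest night only) | 1 - 0 = 1 | 100% |

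**Power, as illustration only.** Borrow 0.60 as an assumed one-night PANAS effect and leave the SD unchanged. Equal weights give 0.60/14 = 0.043 and power of about 5.5%. With w = 0.5 the effect is 0.60 × 0.458 = 0.275 and power is about 25%. If the seven-day average also smooths independent daily noise, a simulation with equal weights gives about 18% without reporting noise and about 6% to 13% with it.

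**The case against.** The strongest reply is that the in-lab wording is inferred, not seen. Survey Information describes each instrument once, for screening and lab use together. For the PSQI it gives a past-month window, although the in-lab version is cut to the preceding night. The PANAS description may be equally generic, and the wording in 3.1 about the day or night before points to a short window. The questionnaires are a separate attachment (section 14). This stands as a limit on confidence. It does not settle the matter, because no text gives the PANAS a shorter window, and the descriptions need reconciling in either case.

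A reader might infer that every PANAS score mixes conditions and that the crossover therefore cannot address affect at all. The documents do not support that. Five of the 14 scores contain at most one condition, and the contrast is reduced, not zero. The POMS-SF, with positive and negative sub-scores, is given at the same times with a momentary frame. A mood survey before the Cognition battery (3.3) and the visual analog scales (section 5 table) add to it.

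A reader might also infer that a null PANAS result will be reported as no effect of noise on mood. Nothing in the plan says so, and POMS-SF results would stand beside it.

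Finally, a momentary frame is only one acceptable choice, and it does not fit a question about how often something was felt. That is accepted, and the fix allows for it.

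**Conclusion.** The point holds as a minor one, with moderate confidence. Under the window as described, PANAS condition contrasts would keep about 7% of a one-night effect with equal recall weights, and 24% to 68% if the latest night carries 30% to 70% of the weight. The 3-in-6 structure comes from the plan's own table. The recall weights, the even spread over earlier nights and the additive form are assumptions. The documents give neither recall weights nor a PANAS effect size, so no PANAS power figure should be read as a property of the plan.

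The damage is confined to what the PANAS adds to the subjective well-being objective. Affect is still assessed through the POMS-SF. No listed endpoint in 3.4 is affected, and the primary endpoint and its power are untouched.

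**What to change.** Reconcile the survey wording in 3.1 (Evening and Morning Procedures), 3.3 (Survey Information; AM and PM Surveys) and 5.2.1. State in 3.3 and 5.2.1 that every in-lab PANAS uses a window that does not reach past the most recent condition night: momentary, or since the last survey. Where the chosen window does not fit a frequency question, adapt the stem and response scale as well as the instruction line. Keep the past-week form for screening only, and do not use that score as the baseline for the in-lab scores. If the in-lab form already has a short window, correct the description in Survey Information and leave the form alone.

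The cost is protocol wording and, if needed, a revised electronic form. The small downside is that screening and in-lab PANAS scores would no longer share a time frame; the in-lab control night can serve as the reference.
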